9.3.2 Exclusion Criteria

Individuals who meet any of the following exclusion criteria are not eligible to participate in the study:

1. Have hypochondroplasia or short stature condition other than ACH (eg, trisomy 21, pseudoachondroplasia)
2. Have any of the following:
 - a. Hypothyroidism or hyperthyroidism
 - b. Insulin-requiring diabetes mellitus
 - c. Autoimmune inflammatory disease (including celiac disease, lupus (SLE), juvenile dermatomyositis, scleroderma, and others)
 - d. Inflammatory bowel disease
 - e. Autonomic neuropathy
 - f. Recent acute illness associated with volume depletion (e.g., nausea, vomiting, diarrhea) that has not completely resolved prior to the first dose of the study drug
3. Have an unstable condition likely to require surgical intervention during the study (including progressive cervical medullary compression)
4. Growth plates have fused
5. Have a history of any of the following:
 - a. Renal insufficiency, defined as creatinine > 2 mg/dl
 - b. Anemia
 - c. Baseline systolic BP < 75 mm Hg or recurrent symptomatic hypotension (defined as episodes of low BP generally accompanied by symptoms i.e., dizziness, fainting) or recurrent symptomatic orthostatic hypotension
 - d. Cardiac or vascular disease, including the following:
 - i. Cardiac dysfunction (abnormal ECHO including abnormal LV mass) at Screening Visit
 - ii. Hypertrophic cardiomyopathy
 - iii. Pulmonary hypertension
 - iv. Congenital heart disease with ongoing cardiac dysfunction

- v. Cerebrovascular disease
 - vi. Aortic insufficiency
 - vii. Clinically significant atrial or ventricular arrhythmias
6. Have the following confirmed ECG findings:
 - a. Right or left atrial enlargement or ventricular hypertrophy
 - b. PR interval > 200 msec
 - c. QRS interval > 110 msec
 - d. Corrected QTc-F > 450 msec
 - e. Second- or third-degree atrioventricular block
 7. Documented Vitamin D deficiency (i.e., concentration of 25-hydroxy-vitamin D in the blood serum occurs at 12 ng/mL or less)
 8. Require any investigational agent prior to completion of study period
 9. Have received another investigational product or investigational medical device within 30 days before the Screening visit
 10. Have used any other investigational product or investigational medical device for the treatment of ACH or short stature at any time
 11. Current chronic therapy with antihypertensive medications, ACE inhibitors, angiotensin II receptor blockers, diuretics, beta-blockers, calcium-channel blockers, cardiac glycosides, systemic anticholinergic agents, any medication that may impair or enhance compensatory tachycardia, diuretics, or other drugs known to alter renal or tubular function
 12. Have been treated with growth hormone, IGF-1, or anabolic steroids in the previous 6 months or long-term treatment (> 3 months) at any time
 13. Have had regular long-term treatment (> 1 month) with oral corticosteroids (low-dose ongoing inhaled steroid for asthma, or intranasal steroids, are acceptable)
 14. Concomitant medication that prolongs the QT/QTc-F interval within 14 days or 5 half-lives, whichever is longer, before the Screening visit
 15. Pregnant or breastfeeding at the Screening Visit or planning to become pregnant (self or partner) at any time during the study.
 16. Have had limb-lengthening or bone-related surgery or expected to have limb-lengthening or bone-related surgery during the study period. Subjects with previous limb-lengthening or bone-related surgery may enroll if surgery occurred at least 18 months prior to the study and healing is complete without sequelae.
 17. Have had a fracture of the long bones or spine within 6 months prior to screening (except for fracture of digits or toes)

BOMARIN [®]	BMN 111-202 Amendment 4	Page 54
----------------------	-------------------------	---------

18. Have AST or ALT at least 3x ULN or total bilirubin at least 2x ULN (except for subjects with known history of Gilbert's disease)
19. Evidence of severe sleep apnea requiring surgery or new initiation of CPAP (based on the screening sleep study)
20. Have current malignancy, history of malignancy, or currently under work-up for suspected malignancy
21. Have known hypersensitivity to BMN 111 or its excipients
22. Has a condition or circumstance that, in the view of the Investigator, places the subject at high risk for poor treatment compliance or for not completing the study
23. Concurrent disease or condition that, in the view of the Investigator, would interfere with study participation or safety evaluations, or would predispose the subject to hypotension (such as recent gastroenteritis or dehydration for any reason)
24. Have abnormal findings on baseline clinical hip exam or imaging assessments that are determined to be clinically significant as determined by the PI
25. Have a history of hip surgery or severe hip dysplasia
26. Have a history of clinically significant hip injury in the 30 days prior to screening
27. History of slipped capital femoral epiphysis or avascular necrosis of the femoral head
28. Are unable to lie flat when in prone position (needed for hip monitoring exam)

Additional Exclusion Criteria for Optional, Open-label Extension Phase:

1. Use of restricted therapies during the initial 6 months of the study
2. Permanently discontinued BMN 111 during the initial 6 months of the study

9.3.3 Removal of Subjects from Treatment or Assessment

Subjects (or their legally authorized representative) have the right to withdraw their consent to participate in the study at any time without prejudice. The Investigator must withdraw from the study any subject who requests to be withdrawn. A subject's participation in the study may be discontinued at any time at the discretion of the Investigator and in accordance with his/her clinical judgment. When possible, the tests and evaluations listed for the termination visit should be carried out.

Investigators or subjects may suspend or discontinue administration of the investigational product. The completeness of the study data may affect the integrity and accuracy of the study results. Therefore, subjects who discontinue study treatment should be encouraged to continue to undergo as many of the protocol-specified procedures and assessments as possible for the remainder of the study, as long as such continued participation does not

detrimentally affect the health, safety, or welfare of the subject. For subjects who discontinue study drug but remain in the study, PK assessments will be waived completely; vital signs and clinical labs/biomarkers will be obtained only once at each visit subsequent to drug discontinuation. Pre-and post-dose designations will not apply as the subject has discontinued dosing and vital sign and clinical lab/biomarkers assessments previously designated as “post-dose” will be waived. All other assessments at each visit should be completed if possible and the subject is willing. Data from the study procedures and assessments may be used to further characterize the natural progression of ACH.

The Investigator (or designee) must contact the BioMarin Medical Monitor before a subject is discontinued by the Principal Investigator (PI) from either the study or from further study treatment. BioMarin reserves the right to discontinue the study at any time for either clinical or administrative reasons and to discontinue participation of an individual Investigator or study site for poor enrollment or noncompliance with the protocol or regulatory requirements.

Reasons for which a subject may be withdrawn from the study or from study treatment by either the Investigator or BioMarin include but are not limited to the following:

- Growth plates have closed
- Subject experiences a serious or intolerable AE
- Subject develops a clinically significant laboratory abnormality
- Subject requires medication or medical procedure prohibited by the protocol
- Subject does not adhere to study requirements specified in the protocol
- Subject was erroneously admitted into the study or does not meet entry criteria
- Subject is lost to follow-up
- Subject becomes pregnant (refer to Section [10.3.1.9](#) for details on the reporting procedures to follow in the event of pregnancy)

If a subject fails to return for scheduled visits, documented effort must be made to determine the reason. If the subject cannot be reached by telephone, a certified letter should be sent to the subject (or the subject’s legally authorized representative, if appropriate) requesting that he or she contact the Investigator. A copy of this letter and any response should be kept in the subject study records. If the subject cannot be contacted or does not respond, the subject will be considered lost to follow-up.

The Investigator (or designee) must explain to each subject before enrollment into the study that the subject’s protected health information, obtained during the study, may be shared with

BioMarin, regulatory agencies, and the IRB or EC; hereafter collectively referred to as the ethics committee (EC). It is the Investigator's (or designee's) responsibility to obtain written permission to use protected health information per country-specific regulations, such as the Health Insurance Portability and Accountability Act (HIPAA) in the United States of America (USA), from each subject (or the subject's legally authorized representative). If permission to use protected health information is withdrawn by the subject, it is the responsibility of the Investigator to obtain a written request from the subject to ensure that no further data will be collected from the subject. The subject will then be removed from the study.

9.3.4 Subject Identification and Replacement of Subjects

Each subject will be assigned a unique subject identifier. This unique identifier will be on all CRF pages.

Subjects who discontinued the study prior to Day 10 may be replaced upon discussion with the DMC. Subjects who discontinued the study after Day 10 of the initial phase will not be replaced.

Duration of Subject Participation

The planned subject participation in this study is 7 months for those subjects who do not continue in the optional, open-label extension phase, and 25 months for subjects who continue. Subjects will receive study treatment daily for 6 months in the initial phase, and 18 months in the optional, open-label extension phase for a total of up to 24 months. Following completion of 6 months, subjects who decline to participate in the extension phase will be followed for safety for an additional 1 month. The safety follow-up assessment will be a telephone call made weekly to the subject's legal guardian to assess for any AEs that may have occurred following completion of dosing. These subjects will return at Day 208 for the Safety Follow-Up visit and exit the study. For subjects who participate in the optional, open-label extension phase, following completion of Month 24, subjects will be followed for safety for an additional month to Month 25. Subjects who participate in the open-label extension phase of study 111-202 will have the option to enroll in the long-term extension study 111-205 at the Month 24/Study Completion Visit. The Month 25 Safety Follow up visit will be waived if a subject enrolls in the 111-205 extension study at the Month 24/Study Completion Visit.

Follow-up assessments and procedures should be performed as outlined in the 111-202 Schedule of Events ([Table 9.1.1](#)).

Subjects who discontinue from study treatment prior to Month 6 will be asked to complete study assessments and procedures for the remainder of the initial phase of the study. Subjects who discontinue from study treatment prior to Month 24 will be asked to complete study assessments and procedures for the remainder of the optional, open-label phase of the study. If subjects discontinue from study treatment and decline to participate for the remainder of the study, they will be asked to return for a final follow-up visit 4 weeks after their last study visit.

Subjects will participate in the study until completion or until one of the following occurs: the subject withdraws consent and discontinues from the study, the subject is discontinued from the study at the discretion of the Investigator or BioMarin, or the study is terminated.

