10.2 Methods and Timing for Capturing and Assessing Safety Parameters

10.2.1 Adverse Event Reporting Period

The study AE reporting period is as follows: after informed consent but prior to initiation of study treatment, only SAEs associated with any protocol-imposed interventions will be reported. After informed consent is obtained and the first administration of study drug, all non-serious AEs and SAEs reporting period begins and continues until 4 weeks following either the last administration of study drug or the early termination visit, whichever is longer. The Month 25 Safety Follow-up Visit will be waived if a subject enrolls in the 111-205 extension study at the Month 24/Study Completion Visit. The criteria for determining, and the reporting of SAEs are provided in Section [10.1.2](#).

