10.4 Reporting Requirements

10.4.1 Expedited Reporting Requirements

All SAEs that occur during the course of the AE Reporting Period (refer to Section 10.2.1), whether or not considered related to study drug, must be reported by faxing the study-specific SAE Report Form to BioMarin Pharmacovigilance (BPV) within 24 hours of the site becoming aware of the event. Each SAE must also be reported on the appropriate eCRF. Investigators should not wait to collect information that fully documents the event before notifying BPV of an SAE. BioMarin may be required to report certain SAEs to regulatory authorities within 7 calendar days of being notified about the event; therefore, it is important that Investigators submit any information requested by BioMarin as soon as it becomes available.

The study SAE reporting period is as follows: after informed consent but prior to initiation of study treatment, only SAEs associated with any protocol-imposed interventions will be reported. After informed consent is obtained and the first administration of study drug, all SAEs must be reported through 4 weeks following either the last administration of study drug or the early termination visit, whichever is longer.

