11.2.9.2 Day 183 Month 6 (± 7 Days)

- Informed consent for optional, open-label extension phase
- Physical examination
- Tanner Stage of Pubertal Development

- Pregnancy test (urine or serum) for female subjects who have begun menses or are ≥ 10 years old
- Vital signs (body temperature, heart rate, BP, respiratory rate)
- Anthropometric measurements
- Weight
- Elbow joint range of motion
- Hip monitoring
- Sleep apnea assessments
- ECG
- ECHO
- Clinical labs (hematology, chemistry, and urinalysis)
- Urine chemistry
- Thyroid function tests
- Serum glucose levels
- Vitamin D
- PD BMN 111 activity biomarkers (all except ANP)
- PD Bone and collagen biomarkers (all)
- Anti-BMN 111 immunogenicity assessment(s)
- PK (full)
- QCT of forearm and tibia
- Bone age x-ray (PA of hand and wrist)
- AP lower extremity radiograph
- Lateral lumbar spine x-ray
- Concomitant medications
- Study drug administration
- Study drug accountability
- Adverse events

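### Children who complete 6 months and decline the extension exit at Day 208, nominally 3 days before their 4-week adverse event reporting period ends

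*Protocol*

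**What the plan says.** **Last dose.** Protocol Section 11.2.9.2 (the Day 183 visit, window ±7 days) lists "Study drug administration" among its procedures. Section 9.1 gives the Day 184 dose only to children who continue into the extension, so a decliner's last scheduled dose is on Day 183.

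**Exit.** For decliners, Section 9.3.4 says they "will be followed for safety for an additional 1 month", by weekly telephone calls to the guardian, and then: "These subjects will return at Day 208 for the Safety Follow-Up visit and exit the study". Section 11.3.1 gives that visit a window of ±7 days.

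**Reporting period.** Under Section 10.2.1 the period for all AEs, serious or not, "continues until 4 weeks following either the last administration of study drug or the early termination visit, whichever is longer". Section 10.4.1 repeats the rule for expedited reporting: "all SAEs must be reported through 4 weeks following either the last administration of study drug or the early termination visit, whichever is longer". Footnote aa to the Schedule of Events also gives 4 weeks. A child who completes the 6 months has no early termination visit, so the last dose sets the clock.

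**Other exit routes in Section 9.3.4.** After Month 24, "subjects will be followed for safety for an additional month to Month 25". Children who stop treatment and decline to stay in the study do so on other terms: "they will be asked to return for a final follow-up visit 4 weeks after their last study visit".

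**The concern.** Safety and tolerability are the primary objective, and the protocol defines the period over which AEs are to be captured. For decliners, the visit that ends participation comes before that period closes. Section 10.2.2 has investigators seek AEs at each patient contact, and no contact is specified after the Day 208 visit. Section 10.6 asks families at the last scheduled visit to report later SAEs that a personal physician thinks may be related to treatment. The rule in Section 10.2.1 is broader: it covers every AE, whatever its seriousness or cause. A non-serious or apparently unrelated event between exit and Day 211 is reportable, but nothing in the schedule prompts anyone to report it.

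The shorter interval does not look intended. Section 9.3.4 describes this route as 1 month of follow-up, and its other two exit routes nominally allow a month or 4 weeks.

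**Working it through.** **Inputs**

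- Last dose for decliners: Day 183, visit window ±7, i.e. Days 176–190 (Sections 9.1 and 11.2.9.2).
- Exit visit: Day 208, window ±7, i.e. Days 201–215 (Sections 9.3.4 and 11.3.1).
- AE/SAE reporting period: 4 weeks = 28 days after the last dose (Sections 10.2.1 and 10.4.1, footnote aa).
- Stated safety follow-up: 1 month, taken here as 30 days (Section 9.3.4).

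**Nominal days**

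- Last dose to exit visit: 208 − 183 = 25 days.
- End of reporting period: 183 + 28 = Day 211. Shortfall: 211 − 208 = 3 days.
- End of a 30-day month: 183 + 30 = Day 213. Shortfall: 213 − 208 = 5 days.

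**Exit-visit window, last dose fixed at Day 183**

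- Permitted exit days: 201 to 215, which is 15 days. The gap runs from 201 − 183 = 18 to 215 − 183 = 32 days.
- Days reaching 28: Days 211–215, so 5 of 15. The other 10 (Days 201–210) fall short.
- Days reaching 30: Days 213–215, so 3 of 15.

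**Both windows, last dose on the day of the Month 6 visit**

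- Let *a* be the displacement of the exit visit and *b* that of the Month 6 visit, each from −7 to +7. The gap is 25 + *a* − *b* days.
- A gap of at least 28 needs *a* − *b* ≥ 3. A difference *d* = *a* − *b* arises in 15 − |*d*| ways, so the count for *d* = 3 to 14 is 12 + 11 + … + 1 = 78.
- There are 15 × 15 = 225 permitted pairs, and 78/225 = 34.7%. This counts permitted day pairs. It does not estimate how often the gap would occur in practice, since visits cluster near their targets.
- Extremes: 201 − 190 = 11 days and 215 − 176 = 39 days. The 11-day gap requires a Month 6 visit at its latest and an exit visit at its earliest.

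**The case against.** The strongest reply is that Section 9.3.4 already covers the period. It states 1 month of safety follow-up and describes that follow-up as weekly AE calls, so the calls could be read as running for the full month and past Day 211. That reading is available, but the same paragraph has the child return at Day 208 and leave the study, and nothing says that calls continue after exit. At best the text is ambiguous.

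Several other points stand and limit the size of the problem:

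- The reporting duty runs from the last dose and does not end at exit. An event on Days 209–211 that becomes known must be reported, and Section 10.5 keeps unresolved AEs under follow-up. The gap is in active questioning about new events.
- The 1-month figure is a rounded planning duration. The 4-week period is the defined AE rule, so 3 days is the firmer shortfall.
- The match on the other exit routes is nominal only. Month 24 has a ±14-day window and Month 25 a ±7-day window, so with a 30-day month that gap can run from 30 − 21 = 9 to 30 + 21 = 51 days. The 4-week route counts from the last study visit, not the last dose. Wide windows are therefore not peculiar to decliners. What is peculiar to them is that the target day itself falls short.
- The safety analysis is descriptive, and no estimate, denominator or stopping rule is shown to change.

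**Conclusion.** The point holds and is minor. As written, the exit visit for decliners is nominally 25 days after the last dose, 3 days before the protocol's own 28-day reporting period closes and about 5 days short of the stated month. A site can follow the schedule exactly and still see the child for the last time too early: 10 of the 15 permitted exit days fall short when the last dose is on Day 183.

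This assumes that the last dose is given at the Day 183 visit, that a completer has no early termination visit, and that the weekly calls stop when the child exits. If the calls were meant to continue, the defect is one of wording.

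The effect on safety conclusions is probably small. The stated half-life is about 45 minutes, the calls cover the time up to exit, and no laboratory or antibody sampling rule is breached. Only children who complete 6 months and decline the extension are affected. The documents do not give their number, and it could be zero.

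**What to change.** Either of two changes makes Sections 9.3.4, 10.2.1, 10.4.1 and 11.3.1 agree:

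1. Time the Safety Follow-Up visit from the actual last dose, at 28 days or later. A nominal Day 213 would do, with an early window of no more than 213 − 211 = 2 days when the last dose is on Day 183.
2. Keep the Day 208 visit and add one documented AE telephone call at 28 days or later after the actual last dose, before the child is recorded as having exited.

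The cost is a change of schedule wording, or one telephone call per child who completes 6 months and declines the extension. The design, endpoints and analyses are unchanged.

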9.4 Treatments

9.4.1 Treatments Administered

Subjects will be administered BMN 111 during the study. The normal dosing schedule is 7 days a week.

9.4.1.1 BMN 111

During the study, subject assigned to receive BMN 111 will be administered one of the following daily dosing regimens:

- Cohort 1: daily morning dose of 2.5 µg/kg BMN 111
- Cohort 2: daily morning dose up to 7.5 µg/kg BMN 111
- Cohort 3: daily morning dose up to 15.0 µg/kg BMN 111
- Cohort 4: daily morning dose 30.0 µg/kg BMN 111

The injection sites should be alternated between doses. Doses may be administered in any of the common SC areas (upper arm, thigh, abdomen, buttocks [refer to Injection Guide for details]). Following administration of each dose, subjects will be observed for a minimum of 30 minutes (longer if clinically indicated) either in the clinic or at the subject's home (by home health nurse or parent or guardian). Instructions for home administration of study drug for subjects who qualify for parent or guardian administration are provided in the BMN 111 Injection Guide and Injection DVD.

9.4.2 Identity of Investigational Product

BMN 111 is cloned into the pJexpress401 vector, expressed in *E. coli* and then purified. The drug substance is a modified CNP peptide that retains wild-type activity and specificity.

The modified CNP sequence is
PGQEHPNARKYKGANCKGLSKGCFGLKLDRIKSMGLGC.

The amino acid sequence is an analogue of the naturally occurring tissue expressed form of C-type natriuretic peptide (CNP53). BMN 111 is a recombinant 39 amino acid peptide that includes the 37 C-terminal amino acids of the human CNP53 sequence, and modified by the addition of the 2 amino acids (Pro-Gly) on the N-terminus. It is a cyclic peptide formed by an intramolecular disulfide bond. The molecular weight of the purified product is 4.1 kDa.

